7.5.2. Clinical Laboratory Tests

Central laboratory test results (chemistry, hematology, coagulation, and urinalysis) at each scheduled visit and change from baseline will be summarized with descriptive statistics.

Shift tables from baseline to each scheduled post-baseline visit will be provided for selected chemistry parameters (ALT, AST, ALP, Total Bilirubin, Creatinine, and Creatinine Kinase) and hematology parameters (Hematocrit, Hemoglobin, Platelets, White blood cell count and differential). For chemistry parameters, the following categories will be used: < the lower limit of normal (LLN), normal, >ULN to $\leq 2 \times ULN$, $\geq 2 \times ULN$ to $\leq 3 \times ULN$, $\geq 3 \times ULN$ to $\leq 5 \times ULN$, $\geq 5 \times ULN$, and missing. For hematology parameters, the following categories will be used: low, normal, high, and missing.

The number and percentage of patients with the following potentially clinically significant abnormal liver function tests at any post-baseline visit will be summarized:

- ALT \geq 3×ULN;
- ALT \geq 5×ULN;

- ALT $\geq 10 \times ULN;$
- AST \geq 3×ULN;
- AST \geq 5×ULN;
- AST $\geq 10 \times ULN;$
- ALT or AST \geq 3×ULN;
- Total Bilirubin >1.5×ULN;
- Total Bilirubin >2×ULN;
- ALP \geq 1.5×ULN;
- ALP $\geq 2 \times ULN$;
- ALT or AST \geq 3×ULN and Total Bilirubin >1.5×ULN;
- ALT or AST \geq 3×ULN and Total Bilirubin >2×ULN; and
- Potential Hy's Law cases: ALT or AST \ge 3×ULN and Total Bilirubin >2×ULN, and ALP \le 2×ULN

A listing of patients with any post-baseline clinically significant abnormal liver function tests will be presented.

All clinical laboratory data will be listed. Values outside the normal ranges will be flagged.

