8.7 Clinical Laboratory Evaluations

Screening laboratory assessments to determine eligibility will be performed at the local laboratory and may have been collected as SOC within the previous 24 hours. Laboratory assessments collected after Screening will be sent to the central laboratory for analysis.

Clinical laboratory assessments (serum chemistry, hematology, coagulation, and urinalysis) will occur at Screening, Baseline (pre-dose), twice weekly during Study Drug Treatment, at EOST, EOT, and 2 and 4 weeks after EOT, or Early Termination. If clinically indicated and at the discretion of the Investigator, or if a suspected adverse event is identified, clinical laboratory assessments may be conducted at any time during the study and compared to Baseline. See Appendix B for a complete list of clinical laboratory analytes.

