9.2.2 Analysis of Safety

All safety analyses will be performed on the Safety Population. Safety data will be patient to clinical review and summarized by appropriate descriptive statistics. A DSMB will be assigned to monitor safety on an ongoing basis throughout the study.

Analyses will be based on adverse events, vital signs, clinical laboratory assessments, and ECGs. Safety analyses will be descriptive and will be presented in tabular format with the appropriate summary statistics.

A TEAE is defined as an adverse event started on or after the administration of study drug. The number and percentage of patients with TEAEs will be tabulated by system organ class, preferred term, and by severity and relationship to treatment. Serious adverse events and adverse events leading to discontinuation from study drug will be summarized. Listings will also be provided for SAEs and adverse events leading to discontinuation of study drug.

Descriptive statistics will be provided for clinical laboratory data for both actual values and changes from Baseline over time.

Descriptive statistics will be provided for vital sign data presented as both actual values and changes from Baseline over time.

Abnormal physical examination findings will be listed.

Descriptive statistics will be provided for ECG interval data and presented as both actual values and changes from Baseline.

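### SAP 7.5.2 gives no ever-abnormal count for creatinine, creatine kinase or hematology, and on plain reading its summary tables for these parameters omit unscheduled results

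*SAP*

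**What the plan says.** **Planned laboratory tables (SAP 7.5.2).** There are three kinds.

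- Descriptive statistics: "Central laboratory test results (chemistry, hematology, coagulation, and urinalysis) at each scheduled visit and change from baseline will be summarized with descriptive statistics".
- Shift tables: "Shift tables from baseline to each scheduled post-baseline visit will be provided for selected chemistry parameters". The chemistry parameters are ALT, AST, ALP, total bilirubin, creatinine and creatine kinase (printed there as creatinine kinase; SAP 6.6.2 lists it as creatine kinase). The same sentence covers hematocrit, hemoglobin, platelets, and white cell count with differential.
- Liver thresholds: patients with "potentially clinically significant abnormal liver function tests at any post-baseline visit will be summarized". This is the only laboratory count taken over the whole post-baseline period.

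All laboratory data are also listed, with out-of-range values flagged.

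**Tests foreseen (Protocol 8.7, repeated in SAP 6.6.2).** Scheduled samples are taken at Screening and Baseline, then "twice weekly during Study Drug Treatment, at EOST, EOT, and 2 and 4 weeks after EOT, or Early Termination". In addition, when clinically indicated "or if a suspected adverse event is identified, clinical laboratory assessments may be conducted at any time during the study". These extra results are to be compared with Baseline.

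**What the protocol asks of the analysis (Protocol 9.2.2).** "Descriptive statistics will be provided for clinical laboratory data for both actual values and changes from Baseline over time". Neither document plans a shift to the worst post-baseline value.

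**The concern.** Two gaps follow from the visit basis of the tables, and each stands without the other.

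1. **No ever-abnormal count.** A set of by-visit tables does not show how many different patients were abnormal at least once. For liver tests the SAP adds that count. For creatinine, creatine kinase and hematology, which it singles out for shift tables, it does not.
2. **Unscheduled results.** A sample taken because someone suspected a problem is more likely than a routine one to be abnormal. If such results are left out of the tables because they do not belong to a scheduled visit, the omission is not random with respect to the value.

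Safety is part of the primary objective (Protocol 2.1), and the study is small, open-label and single-arm. A laboratory tabulation that does not depend on the investigator's judgement of clinical significance is useful there.

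**Working it through.** The plan states no figure to reproduce: there is no formal sample size calculation (SAP 3) and no laboratory hypothesis. The check sets the texts side by side and then adds a little arithmetic for scale.

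**Step 1. Where each kind of result can appear.**

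| Result | By-visit laboratory tables | Any-time laboratory count | TEAE tables | Listing |
|---|---|---|---|---|
| Liver test, scheduled | yes | yes | if reported as an AE | yes, flagged |
| Liver test, unscheduled | no, on plain reading | not stated | if reported as an AE | yes, flagged |
| Creatinine, creatine kinase, hematology, scheduled | yes | none planned | if reported as an AE | yes, flagged |
| Creatinine, creatine kinase, hematology, unscheduled | no, on plain reading | none planned | if reported as an AE | yes, flagged |

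The TEAE column rests on three rules. Protocol 8.1 requires clinically significant laboratory abnormalities to be reported as adverse events, and says that an abnormal value judged not clinically significant is not one. Protocol 8.1.3 grades events by CTCAE v4.03. SAP 7.5.1 tabulates TEAEs by preferred term and by worst grade, counting each patient once per term.

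**Step 2. What by-visit tables can say about ever-abnormal.** Let a_v be the number of patients abnormal at visit v. The number ever abnormal at a scheduled visit, E, is known only to satisfy

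max(a_v) ≤ E ≤ smaller of Σ a_v and n.

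Constructed illustration: three visits each show 1 abnormal patient out of 20. Then 1 ≤ E ≤ 3, so the incidence lies anywhere from 1/20 = 5% (the same patient each time) to 3/20 = 15% (three different patients). The tables do not tell these apart. This gap remains even if every sample is scheduled.

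**Step 3. Scale of one missed patient.** The input is n = 20, the approximate recruitment target (SAP 3), assumed here to be the size of the Safety Population. One patient is 1/20 = 5 percentage points. The exact (Clopper-Pearson) 95% limits for x out of n are

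- lower = the 0.025 quantile of Beta(x, n − x + 1), or 0 when x = 0
- upper = the 0.975 quantile of Beta(x + 1, n − x)

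For x = 0 the upper limit reduces to 1 − 0.025^(1/20) = 0.168. For x = 1 the lower limit reduces to 1 − 0.975^(1/20) = 0.001.

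| Patients counted | Incidence | Exact 95% CI |
|---|---|---|
| 0/20 | 0% | 0 to 16.8% |
| 1/20 | 5% | 0.1 to 24.9% |
| 2/20 | 10% | 1.2 to 31.7% |

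If one patient's only marked abnormality is on an unscheduled sample, the by-visit table gives the first row. A worst-value table that includes unscheduled results gives the second.

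**Step 4. Is the exclusion of unscheduled results certain?** No. Twice-weekly visits are about 7/2 = 3.5 days apart, and Protocol 6.4.2 allows ±2 days, a window 4 days wide. Many extra on-treatment samples would therefore fall inside some visit's window. The SAP gives no rule for mapping samples to visits, and detailed programming specifications are in a separate document (SAP 10). Exclusion is the plain reading of the word scheduled, not an explicit rule.

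**The case against.** The strongest reply is that clinically significant abnormalities are already counted. They must be reported as adverse events whenever they arise, and the TEAE tables then give a patient incidence by worst grade that does not depend on the visit schedule. Tests ordered for a suspected event are the ones most likely to be captured in this way. Every value is also listed and flagged, which is workable to review with about 20 patients. Twice-weekly sampling, and follow-up of clinically significant values until they resolve or stabilise (Protocol 8.1), make it less likely that a peak is seen only once. Finally, the SAP does what Protocol 9.2.2 asks and adds to it.

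Most of this stands, and it rules out three stronger readings that a reader might infer:

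- *That event-triggered results disappear from all non-liver safety tables, or can never contribute to an incidence.* The adverse event route contradicts this.
- *That the laboratory tables are shown to be biased toward normal by a known amount.* The direction is plausible if unscheduled results are excluded. The documents give nothing from which to estimate the size, and the 3/20 case is only an illustration.
- *That the SAP contradicts the protocol.* Protocol 8.7 says that extra tests may be done, "clinical laboratory assessments may be conducted at any time during the study and compared to Baseline", but that describes the conduct of testing and does not promise a table.

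The reply does not close the gap. The adverse event route depends on the investigator's judgement in an open-label trial, and it counts reported terms and grades, not shifts from a baseline category. A listing gives no incidence. The SAP also already accepts the principle of an any-time count for liver tests.

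**Conclusion.** The point holds as a cheap improvement to the plan, not as a defect that threatens its conclusions. For creatinine, creatine kinase and the listed hematology parameters, no laboratory summary table gives the number of patients ever abnormal; that follows directly from SAP 7.5.2. It is a plain-reading inference that unscheduled results for these parameters enter no laboratory summary table. What is then missing from every table is the numeric value or category of such a result and, as an event, any abnormality judged not clinically significant.

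Each patient missed is worth 5 percentage points, assuming 20 patients in the Safety Population. How many would be missed cannot be estimated from the documents and may be none. Whether the liver counts include unscheduled samples is also unstated, so the contrast between liver and other tests on that point is itself only implied.

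**What to change.** Keep the by-visit tables and add the following to SAP 7.5.2.

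1. For each parameter already listed for shift tables, add a shift from baseline to the worst post-baseline value, using all scheduled, unscheduled and Early Termination central laboratory results. Use the highest value for creatinine and creatine kinase. For hematology (hematocrit, hemoglobin, platelets, white cells and differential), show the lowest and the highest separately, because either direction can matter. For the liver parameters already in the list, the worst direction should be stated in the same sentence.
2. State that the liver threshold counts also include unscheduled results.

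The cost is a small amount of extra programming and two or three sentences. No new data are needed and no planned result changes. Protocol 8.7 sends post-Screening samples to the central laboratory, so most results should share one set of reference ranges. If some extra tests are run locally, the SAP should say whether they count; including them would require the local reference ranges.

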APPENDIX C: APACHE II SCORE FORM

	Physiologic Variable	High Abnormal Range					Low Abnormal Range				
		+4	+3	+2	+1	0	+1	+2	+3	+4	
1	Temperature rectal (°C)	≥41	39-40.9		38.5-38.9	36.0-38.4	34-35.9	32-33.9	30-31.9	≤29.9	
2	Mean arterial pressure = (2 x diastolic + systolic)/3	≥160	130-159	110-129		70-109		50-69		≤49	
3	Heart rate (ventricular response)	≥180	140-179	110-139		70-109		55-69	40-54	≤39	
4	Respiratory rate (non-ventilated or ventilated)	≥50	35-49		25-34	12-24	10-11	6-9		<5	
5	Oxygenation A-aDO ₂ or PaO ₂ (mmHg)										
	a)FiO ₂ >0.5:record A-aDO ₂	≥500	350-499	200-349		<200					
	b)FiO ₂ <0.5:record only PaO ₂					>70	61-70		55-60	<55	
6	Arterial pH If no ABGs record serum HCO ₃ below	≥7.7	7.6-7.69		7.5-7.59	7.33-7.49		7.25-7.32	7.15-7.24	<7.15	
7	Serum sodium	≥180	160-179	155-159	150-154	130-139		120-129	111-119	≤110	
8	Serum potassium	≥7	6-6.9		5.5-5.9	3.5-5.4	3-3.4	2.5-2.9		<2.5	
9	Serum creatinine (mg/dL) Double point for acute renal failure	≥3.5	2-3.4	1.5-1.9		0.6-1.4		<0.6			
10	Hematocrit (%)	≥60		50-59.9	46-49.9	30-45.9		20-29.9		<20	
11	White blood count	≥40		20-39.9	15-19.9	3-14.9		1-2.9		<1	
12	Glasgow Coma Scale (see next page) (Score = 15 minus actual GCS)	15 minus the GCS =									
A	Total Acute Physiology Score (APS)	Sum of the 12 individual variable points =									
*	Serum HCO ₃ (venous-mmol/L) Not preferred, use if no ABGs	<52	41-51.9		32-40.9	22-31.9		18-21.9	15-17.9	<15	

Glasgow Coma Scale (Circle appropriate response)		B Age Points	C Chronic Health Points	Apache II Score (sum of A+B+C)

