7. STATISTICAL METHODOLOGY

7.1. General Considerations

7.1.1. Summary Statistics

Summary statistics will be presented in total. For continuous variables, the number of observations (n), mean, standard deviation, median, minimum, and maximum will be provided. For categorical variables, the frequency and percentage in each category will be displayed.

For summary statistics, the mean and median will be displayed to one decimal place greater than the original value and the measure of variability (e.g. standard deviation) will be displayed to two decimal places greater than the original value.

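### Creatinine shifts are tabulated only in multiples of ULN, so no planned table counts patients by rise from their own baseline; add one ratio-to-baseline table

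*SAP*

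**What the plan says.** SAP 7.5.2 plans shift tables from baseline to each scheduled post-baseline visit for "selected chemistry parameters (ALT, AST, ALP, Total Bilirubin, Creatinine, and Creatinine Kinase". One rule covers all of these analytes: "For chemistry parameters, the following categories will be used: < the lower limit of normal (LLN), normal", followed by above ULN to 2x, 2x to 3x, 3x to 5x, and 5x ULN or more, with a category for missing. There is no separate rule for creatinine.

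The other planned laboratory outputs that touch creatinine are:
- Group summaries: results "at each scheduled visit and change from baseline will be summarized with descriptive statistics". Under SAP 7.1.1 this means that n, "mean, standard deviation, median, minimum, and maximum will be provided".
- A by-patient listing of all laboratory values, in which only values outside the normal range carry a flag.

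Patient counts against thresholds are planned for "potentially clinically significant abnormal liver function tests at any post-baseline visit" and for no renal measure. Estimated GFR is in the laboratory panel (Protocol Appendix B, SAP 6.6.2) and gets the group summaries, but it is not among the shift-table analytes.

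**The concern.** ULN multiples suit liver enzymes, where the distance above a population limit carries the signal. A loss of kidney function shows as a rise from the patient's own value, and a patient who starts near the lower limit of normal (LLN) has the most room to rise before leaving the normal band. A shift table built only on ULN multiples can therefore show no movement for a large relative rise, or put a large rise and a trivial one in the same cell.

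Safety is part of the primary objective (Protocol 2.1, SAP 2.1.1). The planned APACHE II categories run to above 30 (SAP 7.3.3), so severe illness is expected. Receipt of hemodialysis is the only exclusion specific to the kidney, although exclusion 17 also lets the investigator exclude for any laboratory abnormality judged an unacceptable risk. A reader of the study report will want to know how many patients had a creatinine doubling on APX001, and no planned table answers that.

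**Working it through.** The plan states no figure to reproduce. The check applies the printed bands to creatinine values.

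**Inputs**
- Bands: SAP 7.5.2, as above.
- LLN and ULN for creatinine: not in the documents, so assumed. The nearest in-document figure is the Protocol Appendix C row "Serum creatinine (mg/dL) Double point for acute renal failure", which gives zero points to 0.6-1.4 mg/dL. That form scores baseline severity and is not a laboratory reference range, so four other ranges were tried.
- Smallest reported step: 0.1 mg/dL (assumed).
- Number of patients: about 20 (SAP 3).

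**Formulas**
- Largest rise that stays normal to normal: ULN / LLN.
- Smallest rise in the cell from normal to above ULN-2x ULN: (ULN + 0.1) / ULN.
- Upper limit of the rise in that cell: 2 x ULN / LLN.

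| Assumed range (mg/dL) | Largest rise with no shift | Smallest rise in first raised cell | Largest rise in that cell |
|---|---|---|---|
| 0.6-1.4 | 1.4/0.6 = 2.33 | 1.5/1.4 = 1.07 | 2.8/0.6 = 4.67 |
| 0.6-1.2 | 1.2/0.6 = 2.00 | 1.3/1.2 = 1.08 | 2.4/0.6 = 4.00 |
| 0.5-1.2 | 1.2/0.5 = 2.40 | 1.3/1.2 = 1.08 | 2.4/0.5 = 4.80 |
| 0.5-1.1 | 1.1/0.5 = 2.20 | 1.2/1.1 = 1.09 | 2.2/0.5 = 4.40 |
| 0.7-1.3 | 1.3/0.7 = 1.86 | 1.4/1.3 = 1.08 | 2.6/0.7 = 3.71 |

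**Examples that hold under all five ranges**
- 0.7 to 1.1 mg/dL is 1.1/0.7 = 1.57-fold and shows as normal to normal.
- 0.7 to 2.1 mg/dL is 2.1/0.7 = 3.0-fold. It shares a cell with 1.1 to 1.5 mg/dL, which is 1.5/1.1 = 1.36-fold.

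**What the other outputs add**
- Mean: one patient rising from 0.6 to 1.2 mg/dL moves the mean of 20 by 0.6/20 = 0.03 mg/dL.
- Maximum change: shows the largest absolute rise at a visit. It gives neither the baseline from which that rise came nor the number of patients with such rises.
- Listing: contains the rise, but a value that ends within the normal range carries no flag.
- Timing: group summaries and shift tables are by scheduled visit, while Protocol 8.7 allows unscheduled tests.

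**Band limits**
As printed, a value of exactly 2x, 3x or 5x ULN satisfies two adjacent bands. A value of exactly 1x ULN falls in one.

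**After the fix**
The three example rises separate: 1.36-fold falls in <1.5x, 1.57-fold in 1.5 to <2x, and 3.0-fold in 3x or more.

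**The case against.** The strongest reply is that renal worsening reaches the report by other routes. Protocol 8.1 requires clinically significant laboratory findings, including significant worsening of those present at Screening, to be reported as adverse events. They are graded by CTCAE, and SAP 7.5.1 counts patients by preferred term and worst grade. With about 20 patients, the maximum change would show a 0.6 mg/dL rise unless another patient rose more, and anyone can count doublings from the listing. Phase 1 is reported to have shown no clinically relevant laboratory changes. All of this stands, and it rules out saying that the plan loses renal signals. What remains is that the adverse event route depends on the investigator's judgment, and the listing leaves the counting to the reader.

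A reader might infer more than the documents support:
- *A tripling will read as low to normal.* This needs a baseline below LLN. A move from 0.4 to 1.2 mg/dL reads that way under four of the five ranges, but not under 0.5-1.1, where 1.2 exceeds ULN.
- *The first raised band spans APACHE II creatinine scores of 0, +2 and +3.* That is so with a ULN of 1.2. With a ULN of 1.4 the band is above 1.4 to 2.8 mg/dL and only +2 and +3 remain. The form is in any case a baseline score.
- *Values will be counted twice.* Only exact multiples are affected, and the symbols may be a PDF-reading slip. The SAP's exposure categories (7.3.6.1, 7.3.6.2) use strict lower bounds, and programming details sit in a separate document.
- *The ULN bands should be replaced.* That would hide baselines that are already raised.

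**Conclusion.** The point holds as a gap in the patient-level safety summary, not in data capture. No planned table counts patients by creatinine rise from baseline. In the ULN shift table, a rise of up to 1.9- to 2.4-fold can show no shift, and one cell mixes rises of about 1.1-fold with rises of up to 3.7- to 4.8-fold. These sizes rest on the five assumed reference ranges. The pattern appears under each of them, but the exact values depend on the laboratory's range. Because every value is listed and clinically significant findings are reported as adverse events, the documents do not support a claim that renal worsening will go unseen. The correction is worth making because it is cheap and safety is part of the primary objective. The band limits are a minor wording check.

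**What to change.** In SAP 7.5.2, keep the ULN shift table and add one table for creatinine in the Safety Population: the number and percentage of patients by highest post-baseline ratio to their own baseline (baseline as in SAP 7.1.3), in the categories <1.5x, 1.5 to <2x, 2 to <3x, and 3x or more, including unscheduled values. The cut-points are a proposal and come from neither document.

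Check the band symbols against the source file and make the lower bounds strict (>2x, >3x, >5x ULN), so that each value has one band. In the same sentence, confirm that the last analyte is the creatine kinase of the laboratory panel.

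The cost is SAP wording and one small table from data already collected, with no change to conduct. There are two downsides. Rises caused by sepsis are counted and cannot be separated from drug effect in a single-arm study. Small absolute rises from a very low baseline also count: 0.4 to 0.6 mg/dL is 0.6/0.4 = 1.5-fold. Reading the new table beside the ULN table limits the second.

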4.2 Exclusion Criteria

Patients who meet any of the following criteria will not be eligible for the study:

1. Neutropenia defined as absolute neutrophil count <500 cells/ μ L
2. Diagnosis of deep-seated *Candida*-related infections causing intraperitoneal candidiasis, septic arthritis, osteomyelitis, endocarditis, myocarditis, meningitis, or central nervous system infection or site of infection that would require antifungal treatment to exceed maximal duration of study drug (14 days)
3. Hepatosplenic candidiasis
4. Blood culture, or any other culture, positive for *C. krusei*
5. Received >2 days (>48 hours) equivalent of prior systemic antifungal treatment at approved doses to treat the current episode of candidemia (e.g., 2 consecutive doses of an echinocandin)

Note: \leq 5 days (\leq 120 hours) equivalent of prior antifungal treatment is permitted for patients with candidemia caused by *Candida* spp. with documented resistance to the specific prior antifungal administered
6. Life expectancy of <72 hours in the opinion of the Investigator
7. Severe hepatic impairment (Child-Pugh Score >9 points) at any time during 2 weeks prior to dosing
8. Patients receiving hemodialysis
9. Known human immunodeficiency virus, active hepatitis B virus, or hepatitis C virus (HCV) infections (defined as hepatitis B surface antigen or HCV ribonucleic acid positivity)
10. Alanine aminotransferase or aspartate aminotransferase \geq 5 \times upper limit of normal (ULN)
11. Total bilirubin >3 \times ULN, unless isolated hyperbilirubinemia or due to documented Gilbert's disease
12. Female patient is pregnant or lactating
13. Inappropriate fungal infection source control (e.g., persistent indwelling catheters or intravascular devices)
14. Investigational drug administered within 30 days prior to dosing
15. Prior participation in this or any previous study of APX001
16. Concomitant use of medication that is a strong inducer of CYP enzymes (e.g., rifampin, carbamazepine, phenytoin, rifabutin, efavirenz, nevirapine, phenobarbital, modafinil, nafcillin, St. John's Wort, and enzalutamide)
17. Any other condition or laboratory abnormality that, in the opinion of the Investigator, would put the patient at unacceptable risk for participation in the study or may interfere with the assessments included in the study

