7.1.3. Baseline Definition

For microbiological data, baseline pathogen(s) are *Candida spp*. isolated from the last positive blood sample collected within 96 hours prior to the first dose of study drug.

For all efficacy and safety endpoints, baseline is defined as the last measurement or assessment prior to the first dose of study drug.

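### Hematology shift tables with one low category cannot show worsening in a patient who enters low, and no planned table summarizes each patient's worst change from baseline

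*SAP*

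**What the plan says.** SAP 7.5.2 plans the following for laboratory data.

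- **Timing of shifts:** "Shift tables from baseline to each scheduled post-baseline visit will be provided".
- **Hematology parameters:** "hematology parameters (Hematocrit, Hemoglobin, Platelets, White blood cell count and differential". The text does not say whether the differential means absolute counts or percentages.
- **Hematology bands:** "For hematology parameters, the following categories will be used: low, normal, high, and missing".
- **Chemistry bands:** several multiples of the upper limit of normal, with a single band below the lower limit.
- **Any-visit thresholds:** for liver tests only, "potentially clinically significant abnormal liver function tests at any post-baseline visit will be summarized", followed by 14 criteria and a dedicated patient listing. Hematology has no counterpart.
- **Descriptive statistics:** "Central laboratory test results (chemistry, hematology, coagulation, and urinalysis) at each scheduled visit and change from baseline will be summarized with descriptive statistics". SAP 7.1.1 includes minimum and maximum in these.
- **Listings:** all laboratory data, with values outside the normal range flagged.

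Under SAP 7.1.3, "baseline is defined as the last measurement or assessment prior to the first dose of study drug". On entry, Protocol 4.2 excludes "Neutropenia defined as absolute neutrophil count <500 cells" per µL. It lists no platelet or hemoglobin limit and leaves other laboratory abnormalities to the Investigator's opinion. Protocol 8.7 adds that, when clinically indicated or when an adverse event is suspected, "clinical laboratory assessments may be conducted at any time during the study and compared to Baseline".

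**The concern.** The entry criteria allow patients whose counts are already below the normal range. For them the hematology shift table has no cell for deterioration: a stable low count and a collapsing one are recorded alike. For everyone else the table separates low from not low, but not mild from severe.

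The tables also stop at scheduled visits. A low point found on an unscheduled test, done because something was suspected, enters no hematology shift table and no threshold count.

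Safety is part of the primary objective (Protocol 2.1). The study has one arm and about 20 patients, so the safety reading rests on individual patients' courses. A table that pairs each patient's baseline with the worst later value is the natural display for that, and the plan does not have one for hematology.

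**Working it through.** The plan states no figure on this point, so there is none to reproduce. The check is to apply the SAP's banding rule to example values.

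**Inputs.** The bands are from SAP 7.5.2 and the 500 cells/µL entry limit is from Protocol 4.2. The documents give no reference range, so the lower limit of normal (LLN) is assumed at 1500, 1800 and 2000 cells/µL in turn, and the upper limit at 7500.

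**Rule.** Low if the value is below LLN, high if above the upper limit, otherwise normal. The last column splits low at 500. The result in each row is the same for all three assumed LLNs.

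| ANC at baseline | ANC later | SAP cell | With low split at 500 |
|---|---|---|---|
| 600, 1000 or 1400 | 450 or 100 | low to low, no shift | 500–LLN to <500 |
| 1400 | 1200 | low to low, no shift | no change of band |
| 3000 | 1200 | normal to low | normal to 500–LLN |
| 3000 | 450 or 100 | normal to low | normal to <500 |
| 12000 | 450 or 100 | high to low | high to <500 |

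Two things follow. Entry at low removes any sight of worsening in this table. Entry at normal or high leaves the shift visible but puts 3000 to 1200 and 3000 to 100 in the same cell.

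**Do the visit-level minimum and maximum fill the gap?** Only in part. The minimum value at a visit is not tied to that patient's baseline. The minimum change picks out the largest absolute fall, which may be a resolving high count. As an illustration, 12000 to 5000 is a change of 5000 − 12000 = −7000, while 600 to 100 is 100 − 600 = −500. The first sets the printed minimum and the second is not seen in it.

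**How likely is such a patient?** Let p be the share of patients who enter low and later fall below 500. The documents give no value, so p is an assumption. The chance of at least one in 20 is 1 − (1 − p)^20:

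- p = 1%: 1 − 0.99^20 = 18%
- p = 2%: 1 − 0.98^20 = 33%
- p = 5%: 1 − 0.95^20 = 64%
- p = 10%: 1 − 0.90^20 = 88%

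**The case against.** The best defense is that the shift table is not the only output. With about 20 patients, an ANC of 100 at a scheduled visit would normally be the printed minimum for that visit. The listing covers all laboratory data, is not confined to scheduled visits, and is short enough to read. Protocol 8.1 asks for clinically significant findings that were present at Screening and then significantly worsen to be reported as adverse events. Protocol 8.1.3 grades these by CTCAE v4.03, and SAP 7.5.1 tabulates them by worst grade. An unscheduled test prompted by a suspected event is already under adverse event review, and the DSMB sees accumulating data. Chemistry, too, has a single band below the lower limit and scheduled-visit shifts. Protocol 1.2 reports no clinically relevant laboratory changes in the Phase 1 studies.

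Much of this stands. A reader might infer from the shift tables that the planned outputs cannot show cytopenia at all; the outputs just listed refute that. The contrast with chemistry is fair only for upward bands and for the liver-test counts.

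It does not close the gap, for three reasons. The listing flags only values outside the normal range, so a patient who is low throughout is flagged alike whether stable or falling. The adverse event route depends on the Investigator judging the finding clinically significant, and laboratory tables should be a check that does not rest on that judgment. Neither route, nor the visit-level minimum, gives a baseline-to-worst summary by patient.

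**Conclusion.** The point holds as a gap in descriptive safety reporting. For a patient who enters low, the hematology shift tables cannot show worsening; for others they show the shift without its depth. Hematology also lacks the any-visit threshold summary that liver tests receive. Other outputs cover this partly, but no planned table summarizes each patient's worst hematology change from baseline.

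Two stronger readings are tempting and not supported:

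- **That any fall below 500 appears as no shift.** This is true only from a low baseline. From a normal or high baseline the fall appears as a shift to low.
- **That the plan ignores its own on-treatment neutropenia limit.** The 500 figure is an entry criterion; the documents set no on-treatment limit.

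The banding result does not depend on which of the three LLNs is assumed. The 18% to 88% range rests wholly on the assumed 1% to 10% share, and the documents do not say how many patients enter low. No efficacy result or analysis population changes. The change is worth making because it is cheap and safety is a primary objective.

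**What to change.** In SAP 7.5.2, add one hematology shift table from baseline to the worst post-baseline value by CTCAE v4.03 grade, which is already the protocol's severity scale. Cover hemoglobin, platelets, white cells, neutrophils and lymphocytes, and include unscheduled results. State that the differential is analyzed as absolute counts; if the laboratory supplies percentages, derive them as white cell count × percentage / 100. Report the number of patients with any post-baseline ANC below 500 cells/µL.

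The minimum alternative is to split the neutrophil low band at 500, used only as a reporting cut-point taken from the entry definition. This shows the falls below 500 but not movement between 500 and the LLN, and it does nothing for the other parameters, so the graded table is preferable.

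The cost is SAP wording and one extra descriptive table, with no added sampling. SAP section 1 places finalization before database lock, so the change belongs there.
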